4.1 General

The ProSpA-CD study will be divided in to two phases:

1. **The ProSpA-CD-Screen phase:** The review of the patients MRE scan for evidence of axSpA.
2. **The ProSpA-CD-Assess phase:** The clinical assessment of case and control subjects for evidence of axSpA in the clinic setting (including clinical examination, PROMs, blood tests, stool sample testing and a dedicated MRI of the spine) followed by comparison of the two groups.

A prospective single-center observational study will be conducted. For the ProSpA-CD-Screen phase of the study, the gastroenterology team at CUH ([name]) will write to approximately 1100 patients with a diagnosis of CD (male and female patients aged 18 years or above) who have had a MRE scan since 2015, asking for their consent to retrospectively review the MRE scans for evidence of axSpA. CD subjects with a known diagnosis of SpA will be eligible and invited to enter the study. Subjects who consent to this will then have their MRE scans reviewed and those with lesions consistent with axSpA (regarded as cases), but who do not have a known diagnosis of SpA, will be referred for further clinical assessment in the NHS rheumatology SpA clinic for evidence of SpA ([name] NHS SpA clinic, but assessed by [name] in a supernumerary capacity). At this stage they will also be invited to participate in the ProSpA-CD-Assess phase of the study.

CD subjects with a known diagnosis of SpA who are already under review by rheumatology and who have lesions on MRE consistent with axSpA will be considered as cases and also invited to participate in the ProSpA-CD-Assess phase of the study. However, they will instead be asked to attend the rheumatology SpA research clinic to be assessed for axSpA as this will be considered to be outside of their routine NHS care ([name] research clinic, but assessed by [name] in a supernumerary capacity).

CD subjects (including those with a known diagnosis of SpA) who had consented to have their MRE scans reviewed, but do not have evidence of axSpA on MRE will also be invited to participate in the ProSpA-CD-Assess phase of the study as control subjects and will be referred for further clinical assessment in the rheumatology SpA research clinic for evidence of axSpA ([name] research clinic, but assessed by [name] in a supernumerary capacity). Cases and controls will be matched for sex and age, with a cases : control ratio of 1:1.

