4.3.2 Assessment of subjects with no lesions on MRE consistent with axSpA (controls)

Subjects (including those with a known diagnosis of SpA) who have consented to having their MRE scans reviewed, but who do not have lesions consistent with axSpA, will be informed in writing of this by the gastroenterology team. They will also be advised that they may be invited to enter the study as a control subject if they are randomly selected through matching (age and sex) to the enrolled 'MRE+ cases' (1:1 ratio). Matched potential control subjects will then be sent an invitation letter, PIS and reply slip (study interest form with a stamped-addressed envelope for returns) by the gastroenterology team to attend the rheumatology SpA research clinic to be assessed by [name] for clinical evidence of axSpA. CD subjects with a known diagnosis of SpA who are already under review by rheumatology and who have lesions on MRE consistent with axSpA will also be invited to attend this clinic for review outside of their routine NHS care but will be considered as cases. Informed consent for study participation in the SpA research clinic will be performed at the start of the consultation. The same clinical assessments, blood and stool samples and dedicated axial MRI scan of the spine and sacroiliac joints will be performed in this control group and in the group of CD subjects with a known diagnosis of SpA who are MRE+ as in the other cases, but will be funded by the research grant unless clinically indicated.

Control subjects in whom there is no evidence of axSpA (by ASAS, modified New York or CASPAR classification criteria) will be informed by letter, which will also be copied to the subjects GP and gastroenterology consultant. Control subjects who do have evidence of axSpA will be informed by letter (also copied to GP and gastroenterology consultant) and asked to return to [name] NHS rheumatology SpA clinic for ongoing care. CD subjects who already have a diagnosis of SpA (both in the control group and cases group) and are already under review by a rheumatology team will be informed by letter of the research clinic outcome and will be followed up as planned by their primary rheumatology team. We will also send a copy of the clinic letter to their GP, gastroenterology consultant and named rheumatology consultant to inform them of the clinic findings and to notify them of any outstanding tests/ management plans that may need to be considered at the next clinic review.

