5.1 Eligibility criteria

5.1.1 Inclusion criteria

- 5.1.1.1 Subjects who are willing and able to give informed consent for participation in the study.
- 5.1.1.2 Male and female subjects aged 18 years or above.
- 5.1.1.3 Diagnosed by the gastroenterology team with Crohn's disease (CD).
- 5.1.1.4 MRE imaging since 2015 for their CD.

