Subjects (including those with a known diagnosis of SpA) without evidence of axSpA on MRE will be contacted by the gastroenterology team (by letter) to inform them of the results and will also be advised that they may be invited to enter the study as a control subject. Once the cases have been identified and enrolled, control subjects will then be randomly selected (age and sex-matched in a case : control ratio of 1:1) to enter the research element of the study. The gastroenterology team will then write to these subjects to invite them to enter the study, accompanied by a PIS and a reply slip (study interest form) with a stamped-addressed envelope to permit the subject to express if they do or do not wish to participate further. Any CD subjects with a history of SpA who have been selected as a potential control subject will be sent a separate invitation letter, PIS and reply slip (study interest form) by the gastroenterology team.

During the clinic consultation for both cases and controls, the research study will be discussed further and the subject will be provided with the opportunity to ask any questions they may have regarding the study. If the subject subsequently agrees to take part in the study, then inclusion and exclusion criteria will be assessed and informed written consent will be taken.

6. Study schedule

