8.2 Statistical analysis

Statistical input has been sought from the University of Cambridge Statistics Clinic (PhD student [name] and his supervisor [name]) and will be supported by [name]. Inter- and intra-rater reliability testing will be performed for the MRE and axial MRI assessments using intra-class correlation coefficients (ICC). The proportion of CD cases with evidence of axSpA on MRE imaging who fulfil diagnostic criteria for axSpA will be expressed as a percentage. Further descriptive analyses will also be performed on study participants. Due to the possible preponderance of patients with axial pain willing to participate in the study and therefore selection bias, we will not be able to calculate the true prevalence of axSpA in CD patients.

As it is expected that the majority of data collected will be count data with an excess of zero-values, a zero-inflated Poisson (ZIP) regression model will be used to test for association between the presence of axSpA, MRE score, PROMs, clinical indices, site of CD and blood biomarkers. In addition, ZIP regression will be used to test for association between MRE scores and those of dedicated axial MRI scans. Zero-inflated binomial regression will be used as appropriate, where the mean approximates the variance. Two-tailed tests will be performed, and the alpha set at 0.05.

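### Matching on MRE result does not balance age and sex by axSpA status, and section 8.2 names no adjustment for either in the axSpA association tests

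*Combined protocol and SAP*

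**What the plan says.** Section 4.1 defines the groups by imaging: "those with lesions consistent with axSpA (regarded as cases". Controls are subjects whose MRE shows no such lesions. The same section sets the matching: "Cases and controls will be matched for sex and age, with a cases : control ratio of 1:1". Section 5.2.2 (consent to enter as a case or control) sets the order: once cases are enrolled, "control subjects will then be randomly selected (age and sex-matched in a case : control ratio of 1:1" for invitation.

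MRE result is not treated as the diagnosis. Both groups go on to clinical assessment and dedicated axial MRI, and section 4.3.2 provides for MRE-negative subjects who turn out to have the disease: "Control subjects who do have evidence of axSpA will be informed by letter". Objective 2 in section 3.2 asks what share of MRE-positive subjects fulfil classification criteria, so some are expected not to.

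Section 8.2 says that zero-inflated Poisson (ZIP) regression "will be used to test for association between the presence of axSpA, MRE score, PROMs, clinical indices, site of CD and blood biomarkers". It does not say which of these is the outcome, and it mentions no covariate. No other section supplies one. Eligibility in section 5.1.1 is wide: "Male and female subjects aged 18 years or above". Appendix 2 lists demographics among the data collected.

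**The concern.** The plan matches on age and sex, and so treats them as factors worth controlling. The control applies to one grouping (MRE result), while the association tests in 8.2 use another (presence of axSpA). The second grouping cuts across the matched pairs. When an MRE-positive subject does not have axSpA, that subject and, usually, the matched control both land in the axSpA-negative group. If such subjects differ in age or sex from MRE-positive subjects who do have axSpA, the matched control carries the same difference into the axSpA-negative group a second time.

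Measures such as function, spinal mobility and ESR could plausibly vary with age or sex. An age or sex difference could then be reported as a feature of axSpA in Crohn's disease, or could hide a real one. What is at stake is the PROM, index and biomarker tests and objectives 4 and 5.

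**Working it through.** The plan gives no figure on this point to reproduce. The check has three parts.

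**Inputs from the documents.** 66 cases and 66 matched controls (8.1), hence 132 subjects; 1:1 matching on age and sex (4.1); two-sided alpha 0.05 (8.2).

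**Assumed inputs (not in the documents).** *p* = share of MRE-positive subjects with axSpA (PPV): 50%, 70% or 90%. *q* = share of controls with axSpA: 8%. Age SD 13 years. *g* = years by which MRE-positive subjects without axSpA are older than those with it: 0 to 15. *r* = correlation of the measure with age: 0.1 to 0.5. The measure has no true relation to axSpA.

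**1. Age gap by axSpA status under perfect age matching.** Take the mean age of MRE-positive subjects with axSpA as zero. The mean age of MRE-positive subjects without it is *g*, and controls average (1−p)g.

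- Mean, axSpA-negative = [(1−p)g + (1−q)(1−p)g] / [(1−p) + (1−q)]
- Mean, axSpA-positive = q(1−p)g / (p+q)

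For p = 0.70, g = 10: (3 + 0.92×3)/(0.30 + 0.92) = 5.76/1.22 = 4.72; 0.08×3/0.78 = 0.31; gap = 4.4 years.
For p = 0.50, g = 15: (7.5 + 6.9)/1.42 = 10.14; 0.6/0.58 = 1.03; gap = 9.1 years.
For p = 0.90, g = 15: (1.5 + 1.38)/1.02 = 2.82; 0.12/0.98 = 0.12; gap = 2.7 years.

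**2. Type I error of an unadjusted test by axSpA status.** Simulation of 66 pairs, 4,000 repeats per scenario, control age within 2 years of the case, t-test as a stand-in for ZIP:

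| PPV | g (years) | Age gap (years) | Rejects, r = 0.3 | Rejects, r = 0.5 |
|---|---|---|---|---|
| 90% | 10 | 1.8 | 5% | 5% |
| 90% | 15 | 2.7 | 6% | 6% |
| 70% | 5 | 2.2 | 5% | 6% |
| 70% | 10 | 4.4 | 8% | 13% |
| 70% | 15 | 6.6 | 12% | 22% |
| 50% | 15 | 9.1 | 15% | 34% |

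With r = 0.1, rejection stays between about 5% and 6% throughout. With g = 0 there is no inflation. With age in a linear model, rejection is about 5% in every scenario. Repeat runs agreed to within about 2 percentage points.

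A second set-up had age raise the odds of axSpA within each MRE group, with axSpA in 50% of MRE-positive and 10% of MRE-negative subjects. The direction is opposite (axSpA subjects older), so it does not confirm the table's values, but the pattern is the same. At an odds ratio of 1.5 per SD of age, rejection was 8% (r = 0.3) and 12% (r = 0.5); at 2 per SD, 14% and 28%. Adjusted, it was about 4% to 6%.

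**3. Sex, by exact calculation.** Assume 50% male in both MRE groups, exact matching, axSpA in 50% and 10%, and an odds ratio of 2 for axSpA in men within each group. The probabilities of axSpA are then 0.586 (men) and 0.414 (women) if MRE-positive, and 0.130 and 0.070 if MRE-negative.

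- Male share, axSpA-positive: (0.586 + 0.130)/1.2 = 59.7%
- Male share, axSpA-negative: (2 − 0.716)/2.8 = 45.9%

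The gap is about 14 points. It is zero at an odds ratio of 1, and about 4 points at an odds ratio of 2 when axSpA is present in 90% and 2%: it shrinks as MRE approaches a perfect marker of axSpA.

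**The case against.** A reader might infer that the study matched on the wrong variable. The documents do not support that. Section 4.1 describes a comparison of the case and control groups, and matching on MRE result suits it. AxSpA status could not have been used, because controls are chosen after the MRE is read and before anyone is assessed. Nor does 4.1 claim that the matching controls age and sex in the axSpA comparison, so it has nothing to correct.

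A reader might also infer that 8.2 rules out age and sex. It does not: it is silent. It lists variables without assigning outcome and predictor, and the regression it plans can hold covariates. What stands is that, followed as written, the tests leave the matching factors uncontrolled, and any adjustment would be chosen without prior commitment.

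The strongest objection is to the size. No document figure supports any PPV, age gap or correlation used above, and the linear tests are not ZIP models. Material inflation needs a low to moderate PPV, a large age gap and a moderate to strong age correlation together. This stands, and it limits the point to a possible bias of unknown size.

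It is also fair that unadjusted estimates are legitimate for describing phenotype (objective 4) and for asking whether disease site predicts axSpA (objective 5). They should be kept beside the adjusted ones.

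**Conclusion.** The concern holds as a gap in the planned association models. Matching by MRE result does not guarantee balance by axSpA status, and 8.2 names no adjustment for age or sex where axSpA status is the grouping. Confounding is possible, not certain: age or sex must relate both to axSpA within MRE groups and to the measure tested. Under the assumptions shown, type I error lies between about 5% (high PPV, small age gap or weak age correlation) and 34% (PPV 50%, 15-year gap, correlation 0.5), and is about 5% with age in the model. The upper end illustrates the mechanism and should not be read as an expected error rate. A reader might extend the point to the study's main aim, but sensitivity and specificity are not its subject. The change is worth making because it costs almost nothing and uses factors the plan already chose to control.

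**What to change.** In section 8.2, state that the association models involving axSpA status include age (continuous) and sex as covariates, with unadjusted estimates shown alongside. Tabulate age and sex by axSpA status as well as by MRE result, so that readers can see whether the balance carried over.

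The cost is a sentence or two and one table. Demographics are already collected. Two covariates use two degrees of freedom in a single-part model and up to four in a ZIP model (two in the count part, two in the zero part), in about 132 subjects. Neither the matching nor section 4.1 needs to change.

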4.2 ProSpA-CD-Screen phase

4.2.1 MRE review

The MRE scans at CUH are typically performed using both an oral contrast agent and intravenous Gadolinium to diagnose and assess the extent of CD. The images also capture the lower thoracic spine/ thoracolumbar junction and lumbar spine in the coronal plane and sacroiliac joints in coronal and axial planes. It is the coronal and axial images of the sacroiliac joints that we will be using to assess for evidence of axSpA (sacroiliitis). There are a number of different sequences included for the MRE scans at Addenbrookes hospital including the SSFSE FS (single shot fast spin echo fat suppressed) and LAVA FLEX sequences which are fat suppressed (the complete list of MRE sequences used can be found in Appendix 4).

For the subjects who consented to have their MRE imaging reviewed, two trained scorers (one musculoskeletal radiologist, [name]; one rheumatologist, [name]) will assess MRE imaging (sacroiliac joints) for evidence of axSpA using a specifically designed scoring system (see below). The MRE assessors will be blinded to the subjects co-morbidities (other than CD). Training sessions for this will be delivered by a consultant musculoskeletal radiologist ([name]). This scoring system was developed by an expert musculoskeletal radiologist ([name]) for this study to specifically identify features of sacroiliitis on both MRE and dedicated MRI spine images, and should permit reliable intergroup comparisons. It has not yet been used in clinical practice due to a lack of previous research on this topic. Scores will be compared and discrepancies decided by consensus. If the two assessors ([name]) are unable to reach a consensus for a particular subject, [name] (considered the 'gold-standard' scorer) will be asked to review and score the images. [name] will be one of the two expert consultant musculoskeletal radiologists who will be reviewing and scoring the subsequent dedicated axial MRI scans and therefore to prevent any scoring bias, the MRE images reviewed by [name] in the ProSpA-CD-Screen phase will be anonymised (patient identifiable data removed). The site of CD involvement in the gut will also be reviewed and documented, for further analysis.

Training will also be provided to identify significant sacral fractures and significant infiltrative bone lesions. If an unexpected finding of this sort should arise, the imaging will be reviewed by the

consultant musculoskeletal radiologist ([name]) and appropriate onward referrals and communication with the patient will be made.

Prior to the commencement of MRE screening, both scorers will score the same ten MREs to determine inter-rater agreement. Both scorers will then score the same ten MREs on two separate occasions a month apart, to determine intra-rater agreement.

The scoring system for sacroiliac joints on MRE imaging will be divided into two sections as follows:

- i) Joint margins and contour (score range 0 – 2; 0=normal, 1=mildly abnormal, 2=severely abnormal)
- ii) Juxta-articular bone marrow signal (score range 0 – 3; 0=normal, 1=mild, 2=moderate, 3=severe)

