8.1 Power analysis

This study will aim to include all CD cases with MRE imaging since 2015; the estimated sample size is therefore 1100 cases.

To our knowledge, there are no studies comparing the sensitivity and / or specificity of MRE scans with gold standard dedicated MRI for the detection of sacroiliitis. However, there have been some studies comparing CT imaging with MRI and these found MRI to be up to 17% more sensitive for the detection of sacroiliitis than CT [48, 49].

Although MRE is expected to be more sensitive at detecting evidence of sacroiliitis than CT, our power calculation is based on the conservative estimate that MRE will detect at $\geq 60\%$ (sensitivity) of

the cases of sacroiliitis, when compared with the gold standard dedicated axial MRI scan. Therefore with 80% power and a two-tailed alpha of 0.05, it is estimated that ≥ 60 control subjects (MRE normal) will be required for the study. It is estimated that a sample of >60 cases (with abnormal MRE scans) would be needed since the sample size required to assess specificity for a screening test is less than that of sensitivity. Case and controls will be recruited in a ratio of 1:1. From the 1100 MRE scans already performed, it is expected that $\geq 90\%$ will have a diagnosis of CD, i.e. 990 subjects. We estimate that $\geq 50\%$ of postally invited participants will consent to participate in the study, giving approximately 445 MRE scans for review.

The two previous studies assessing IBD patients for evidence of sacroiliitis using MRE imaging estimated the prevalence to be 16.7% and 15% [27, 28]. We therefore estimate to recruit ≥ 66 subjects with positive MRE scans (cases) and ≥ 66 matched controls. This is a conservative estimate, greater than the minimum number needed to recruit.

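### MRE inter-rater agreement rests on ten pre-study scans, the only reliability sample named, while paired scores on about 445 study scans are not planned to be kept or analysed

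*Combined protocol and SAP*

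**What the plan says.** Section 4.2.1 (MRE review) describes a two-part score for the sacroiliac joints, 0 to 2 for joint margins and 0 to 3 for marrow signal. It was built for this study, and of its status the protocol says: "It has not yet been used in clinical practice due to a lack of previous research on this topic".

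Reliability is to be assessed before screening starts: "both scorers will score the same ten MREs to determine inter-rater agreement". For repeatability: "Both scorers will then score the same ten MREs on two separate occasions a month apart, to determine intra-rater agreement". How the ten scans are chosen is not stated.

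The same section sets out the main reading: "For the subjects who consented to have their MRE imaging reviewed, two trained scorers", one a musculoskeletal radiologist and one a rheumatologist, assess the images. Then: "Scores will be compared and discrepancies decided by consensus", with a third reader where the two cannot agree. Section 8.1 (Power analysis) expects this to cover several hundred scans, "giving approximately 445 MRE scans for review".

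Section 8.2 (Statistical analysis) states: "Inter- and intra-rater reliability testing will be performed for the MRE and axial MRI assessments", by ICC. It gives no number of scans, form of ICC, confidence interval or target value.

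**The concern.** The MRE score is the index test for objective 1 (validity, sensitivity, specificity and AUC), and it decides who enters the second phase as a case or a control. It has no track record, and its two scorers come from different specialties. A reader of the results will want to know how far two trained people agree when they apply it.

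The only sample the plan names for that question is ten scans read before screening. An ICC from ten pairs is very imprecise unless agreement is excellent. A pre-study exercise also cannot show whether agreement holds once screening is under way.

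Routine conduct of the study produces a far larger set of paired readings. If the two scores are replaced by the consensus score and not kept, that information is lost and cannot be recovered later.

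**Working it through.** **Inputs from the protocol.** Ten scans and two scorers (4.2.1). About 445 scans for review (8.1). MRE positivity of 15% to 16.7% from the two earlier MRE studies (8.1). Two-sided alpha 0.05 (8.2), hence 95% intervals. Excess of zero scores expected (8.2).

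**Assumption.** The true ICC is not given, so 0.6, 0.8 and 0.9 are used as a range.

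**Step 1: the number of paired readings.** Section 8.1 starts from 1100 scans, 90% with Crohn's disease and 50% consent: 1100 × 0.90 × 0.50 = 495, not 445. Applying the 90% twice gives the stated figure: 990 × 0.90 × 0.50 = 445.5. The choice does not matter here, since with 495 scans the interval limits below move by less than 0.005.

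**Step 2: precision of the ICC.** For a one-way, single-reader ICC r with k = 2 readers and n scans:

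- F = (1 + r)/(1 − r)
- F_L = F / F₀.₉₇₅(n − 1, n) and F_U = F × F₀.₉₇₅(n, n − 1)
- limits = (F_L − 1)/(F_L + 1) and (F_U − 1)/(F_U + 1)

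Worked case, r = 0.8 and n = 10: F = 1.8/0.2 = 9. The F quantiles are 3.779 on (9, 10) and 3.964 on (10, 9) degrees of freedom. F_L = 9/3.779 = 2.38, so the lower limit is 1.38/3.38 = 0.41. F_U = 9 × 3.964 = 35.7, so the upper limit is 34.7/36.7 = 0.95.

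| Assumed ICC | 95% CI, n = 10 | Width | 95% CI, n = 445 | Width |
|---|---|---|---|---|
| 0.6 | 0.03-0.88 | 0.85 | 0.54-0.66 | 0.12 |
| 0.8 | 0.41-0.95 | 0.54 | 0.76-0.83 | 0.07 |
| 0.9 | 0.67-0.97 | 0.31 | 0.88-0.92 | 0.04 |

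The consistency form of the ICC gives slightly lower limits at n = 10 (0.38 at ICC 0.8, 0.65 at ICC 0.9).

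**Step 3: positives among ten scans, if unselected.** With X ~ Binomial(10, 0.15), the expected number is 10 × 0.15 = 1.5. P(X = 0) = 0.85¹⁰ = 0.197. P(X ≤ 1) = 0.197 + 10 × 0.15 × 0.85⁹ = 0.197 + 0.347 = 0.544. At 16.7% the two probabilities are 0.161 and 0.483. These figures apply only if the ten are a random draw, which the protocol does not say.

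**Step 4: check on the normal-theory intervals.** A 0-to-5 zero-heavy score was simulated at 15% positivity, with latent between-reader correlations of 0.80, 0.90 and 0.95. With ten scans, both readers scored every scan zero, leaving the ICC undefined, in about 11% to 14% of samples. Among the rest, the central 95% of estimates ran from about −0.1 to 1.0. With 445 scans it ran 0.51-0.74, 0.70-0.86 and 0.82-0.92. The intervals in step 2 are therefore optimistic at both sample sizes, but the contrast between them remains.

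**The case against.** The strongest reply is that section 8.2 does not confine the ICC to ten scans. Its sentence also covers the axial MRI, for which no ten-scan exercise is described, so study readings may be meant for both. The ten-scan exercise is placed before screening, and Appendix 3 lists score training and the reliability exercise separately from scoring the scans, so it can be read as calibration. This stands in part. A reader might infer that the paired study readings will be discarded, and the documents do not say so. But they do not plan to use them either, and section 4.2.1 gives determining agreement as the purpose of the ten scans.

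Other stronger readings also go too far:

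- **That the ten scans will hold few or no positives.** The selection method is not stated. If they were chosen to span the score range, step 3 would not apply. The widths in step 2 would still be those of ten pairs.
- **That independent pairs will certainly exist.** Section 4.3.3 calls the axial MRI readers independent. Section 4.2.1 does not use that word for the MRE scorers. Comparing scores implies two separate scores, but independence and retention both need to be written down.
- **That ten scans tell one nothing.** At a true ICC of 0.9 the lower limit of 0.67 carries some information.
- **That poor single-reader agreement would invalidate the accuracy results.** The index result is the consensus score, with a third reader if needed. A single-reader ICC is not the reliability of that result. Inter-rater reliability is not a listed objective, and no decision rule depends on it.

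**Conclusion.** The point holds as a cheap improvement to the analysis plan. Ten is the only sample size given for MRE reliability. At an assumed ICC of 0.8, the interval from ten scans is 0.54 wide, against 0.07 from the 445 scans that both scorers are due to read. Across assumed values of 0.6 to 0.9 it is roughly seven to nine times wider.

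The size rests on an assumed ICC and on normal-theory intervals, which understate the uncertainty for this score. It also assumes that the two scorers read separately before comparing, which the text implies but does not state. The 20% chance of no positive scan and the 54% chance of at most one are conditional on unselected scans at 15% positivity. The finding is that the plan leaves the better sample unnamed and unprotected, not that it excludes it.

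**What to change.** 1. **Section 4.2.1:** keep the ten-scan exercise and describe it as pre-study calibration. State how the ten scans are chosen.
2. **Section 4.2.1:** require each scorer to score every MRE independently and to record the two component scores, and a positive/negative call, before scores are compared. The section gives no score cut-off for a positive MRE, so say how that call is made.
3. **Section 8.2:** estimate inter-rater agreement from the pre-consensus scores on all reviewed MREs, for the score and for the positive/negative call, with 95% confidence intervals. Name the form of ICC, and use kappa for the binary call. State that this is single-reader agreement, not the reliability of the consensus result.
4. **Intra-rater agreement:** the main study gives one reading per scorer, so this still needs a planned re-read, preferably of more than ten scans. If that set is chosen to include more abnormal scans, state that its ICC is not directly comparable with the inter-rater ICC in unselected scans, because the spread between scans is larger.

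For inter-rater agreement (items 1 to 3) the cost is wording, extra database fields and a little more analysis, with no extra readings. Enlarging the intra-rater set would add re-reads; changing only which scans are re-read would not.
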